9.2 Definitions

Adverse Event: Any untoward medical occurrence in a human subject, including any abnormal sign, symptom, or disease, temporally associated with the subject's participation in research, whether or not considered related to the subject's participation in the research.

Protocol Deviation: Any change, divergence, or departure from the IRB approved study procedures in a research protocol. Protocol deviations are designated as serious or non-serious and further characterized as:

- Those that occur because a member of the research team deviates from the protocol.
- Those that are identified before they occur, but cannot be prevented.
- Those that are discovered after they occur

9.3 Reporting Protocol deviations, AEs and Deaths

Anticipated deviations in the conduct of the protocol will not be reported to the IRB unless they occur at a rate greater than anticipated by the study team. Expected adverse events will not be reported to the IRB unless they occur at a rate greater than that known to occur in those having phlebotomy procedures normally. If the rate of these events exceeds the rate expected by the study team, the events will be classified and reported. Deaths related to the natural history of hepatitis will be reported at the time of continuing review (see annual reporting to the IRB).

9.3.1 Expedited Reporting to the IRB

Any reportable new information (RNI) will be reported to the IRB within 5 business days. This includes:

- 1) Information that indicates a new or increased risk, or a safety issue.
- 2) Any harm experienced by a subject or other individual, which in the opinion of the investigator are unexpected and probably related to the research procedures.
- 3) Non-compliance with the federal regulations governing human research or with the requirements or determinations of the IRB, or an allegation of such non-compliance.
- 4) Failure to follow the procedure due to the action or inaction of the investigator or research staff.
- 5) Breach of confidentiality.
- 6) Change to the protocol taken without prior IRB review to eliminate an apparently immediate hazard to a subject.
- 7) Incarceration of a subject in a study not approved by the IRB to involve prisoners.
- 8) Complaint of a subject that cannot be resolved by the research team.
- 9) Premature suspension or termination of the research by the sponsor or the investigator.
- 10) Audit, inspection, or inquiry by a federal agency.
- 11) Written reports of study monitors.

9.3.2 Waiver of Reporting Anticipated Protocol Deviations, Expected non-UP AEs and Deaths

Deviations in the protocol that do not rise to the level of serious or continuing non-compliance, and unanticipated or adverse events that are NOT serious, unexpected AND related to research protocols need not be reported in an expedited manner to the IRB. Rather, such RNI should be reported as a group at the time of annual renewal (see below).

9.4 Annual Reporting to the IRB

The following items will be reported to the University of Maryland IRB in summary at the time of Continuing Review:

- Serious adverse events or deaths that are not related to the research
- All adverse events associated with research including expected AEs Protocol deviations. This includes AEs related to phlebotomy within 48 hours of procedure.
- Serious, continuing, and minor non-compliance
- Any trends or events which in the opinion of the investigator should be reported
- Any study participants incarcerated while on active HCV treatment that were provided their remaining HCV medications in the jail/prison

9.4.1 Type and Duration of the Follow-up of Subject after Adverse Events

All SAEs and non-serious AEs identified in this study will be followed until resolution or until the PI judges the AE/SAE has stabilized and no more follow-up is required. This requirement indicates that the follow-up may be required for some events after the participant discontinues participation from the study. These events will be reported to the IRB annually.

10 Withdrawal of a Subject

A participant may withdraw from the study at any time. As part of their duties to ensure that research participants are protected, the IRB, IIV, or other government agencies may discontinue the study at any time. Voluntary withdrawal from the protocol may occur at any time at the request of either the participant or the PI. If a request is made to withdraw from the protocol, all further planned study procedures will be immediately cancelled and further follow-up will be terminated. Samples and data collected already collected may be used.

If a patient becomes pregnant during the course of the study, the patient will be discontinued from the study.

10.1 Return of Withdrawn/Removed Subjects

A participant who has withdrawn may not return to the study.

11 Remuneration Plan for Subjects

Participants will not be renumerated for receiving HCV treatment.

Participants will not be renumerated for standard of care PrEP or buprenorphine.

Participants will receive \$25 remuneration as gift cards at those visits where HIV risk assessment and stored sample blood draws are completed. Those 7 visits are Screening, Week 4, Week 12, Week 24, Week 48, Week 72 and Week 96 only. For adherence visits for PrEP which DO NOT coincide with HIV risk assessment or stored sample visits, participants will receive \$25 renumeration as gift cards for those visits. This would be a maximum of 6 additional visits at \$25/visit. We will encourage combined visits.

Participants who choose to enroll in the GMA will be renumerated as follows:

Compensation for GMA data collection	A) Weeks 1-24 Participants can receive a total of \$480 between weeks 1-24 for answering random daily prompts based on how many prompts they answer in each week: Answering 1-7 prompts/week = \$5 Answering 8-14 prompts/week = \$10 Answering 15-21 prompts/week = \$15 Answering 22-28 prompts/week = \$20 B) Weeks 25-48	Up to \$920.00
--------------------------------------	--	----------------

	
Participants can receive a total of \$240 between weeks 25-48 for answering random daily prompts based on how many prompts they answer each week:
 
Answering 1-3 prompts/week = \$5
 
Answering 4-7 prompts/week = \$10
 
C) End of Study Week 48
 
Participants can receive up to \$200 for returning the smartphone in working condition at Week 48, to be pro-rated by week for those participants who do not complete 48 weeks of the study,
	
--	--	--

12 Monitoring

As this is an observational study with intervention limited to blood and epidemiologic data collection, safety issues are not expected. PI and the study team will conduct regular monitoring of safety on a weekly basis and report to the IRB as specified in section 9.

13 Statistical Considerations

13.1 Description of the Analyses

The primary outcome is achievement of SVR12 in phase 1 (first 100 enrolled participants). The primary analysis of efficacy for phase 1 is intention-to-treat for the proportion of patients who achieve SVR along with exact two-sided 95% confidence intervals, overall and by sub-categories. All patients who receive at least one dose of direct acting antiviral are included in the intention-to-treat analysis and patients without follow-up data are considered to have treatment failure. Chi-squared or Fisher's exact test will be used to assess the association of SVR12 with baseline characteristics such as HIV-status, as well as on treatment factors such as medication adherence and OST status. Percentage and standard error will be calculated for each of the secondary outcome of PrEP and buprenorphine including uptake, adherence, and retention. In phase 2, participants without recent IDU (opioid misuse within 1 year but not within 3 months) will be compared to patients with recent IDU, and the impact of collocated OST vs non-collocated OST will be assessed.

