1.1 Background Information

Hepatitis C virus (HCV) is a serious infection that chronically infects approximately 135 million people worldwide.(1) There is ongoing acute transmission of HCV, especially in young people who inject drugs,(2) and human immunodeficiency virus (HIV) infected men who have sex with men.(3) Chronic infection with HCV can lead to cirrhosis, liver cancer, and death, and is the leading cause of liver transplantation in the United States.(4) HCV is treatable, and the goal of treatment is to achieve a sustained virologic response (SVR), considered to be a functional cure (absence of plasma HCV RNA 12 weeks after completing therapy). Historically, treatment of HCV using interferon-alfa involved significant toxicities and poor rates of SVR, particularly in patients with HIV and/or black race.

The advent of direct-acting antivirals (DAA) has been revolutionary in the advancement of HCV treatment. DAAs have few side effects, short durations of treatment, and high SVR. In addition, they are effective regardless of race, gender, or HIV status, leaving few barriers to treatment. (5, 6) Therefore, in HCV infected individuals, DAAs have the potential to lower mortality, improve quality of life, reduce long-term costs of complications and interrupt the current global HCV epidemic.(7)

Although DAAs have been extremely effective in curing existing HCV infections, there continues to be transmission of HCV. In 2013, there were an estimated 29,718 cases of acute HCV in the U.S. (8). This acute epidemic of HCV is being driven by individuals with high risk practices, including people who inject drugs (PWID) and men who have sex with men (MSM) (9, 10). Many of these individuals lack access to providers and treatment for HCV (11). Therefore, the current barrier to eradicating HCV is implementing accessible treatment programs in high-risk populations in order to effectively cure those who are chronically infected, in order to prevent transmission of disease.

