2.1 Primary Objective

Efficacy of DAA for treatment of HCV in people with ongoing injection drug use.

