2.3 Exploratory Objective

1. Rate of HCV reinfection after treatment with DAAs
2. Rates of new HIV infection
3. Immunologic and virologic studies
4. Evaluate adherence to HCV medications
5. Evaluate the psychological, social, and behavioral factors related to drug use
6. Evaluate the impact of collocation of OST on HCV treatment outcomes

3 Study Design

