6.3.7 Viral sequencing

Individuals with new seroconversion to HIV will have sample sent for viral sequencing and phylogenetic analysis. Individuals with detectable HCV RNA after completion of HCV treatment or new infection during the follow up period will have current sample, and baseline stored sample sent for viral sequencing and phylogenetic analysis. Phylogenetic analysis will enable us to demonstrate mode of transmission of new infections and resistance associated variants that may impact ART and DAA therapy in the future.

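### Section 13.1 does not use the planned sequencing to interpret viraemia at SVR12, so reinfection before that test lowers the estimate of DAA efficacy

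*Combined protocol and SAP*

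**What the plan says.** The primary objective (Section 2.1) is "Efficacy of DAA for treatment of HCV in people with ongoing injection drug use". Section 13.1 sets the endpoint: "The primary outcome is achievement of SVR12 in phase 1 (first 100 enrolled participants". The analysis set is broad: "All patients who receive at least one dose of direct acting antiviral are included in the intention-to-treat analysis". The one failure rule that Section 13.1 spells out concerns missing data: "patients without follow-up data are considered to have treatment failure". SVR itself is defined only in the background (Section 1.1), as "absence of plasma HCV RNA 12 weeks after completing therapy".

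Reinfection appears separately, as the first exploratory objective in Section 2.3: "Rate of HCV reinfection after treatment with DAAs". No case definition and no start of time at risk are given for it.

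Section 6.3.7 describes who is sequenced: "Individuals with detectable HCV RNA after completion of HCV treatment or new infection during the follow up period". For these people both the current sample and the stored baseline sample are sent for sequencing and phylogenetic analysis. The stated purpose is to learn about transmission routes and resistance variants. Section 8, item A, adds that HCV sequences may be compared for how closely they are related. Section 13 refers to neither.

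**The concern.** Detectable RNA at the SVR12 test can arise in two ways. The baseline virus may have persisted or returned, which is a failure of the DAA. Or the participant may have been cured and then infected again, which is not. An endpoint based on RNA alone cannot tell these apart, and Section 13.1 has no rule on the origin of the virus.

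In many trials this would hardly matter. Here phase 1 enrols people who injected within three months of screening (Section 4.2), so re-exposure after therapy is to be expected. Section 13.2 takes its 90% reference from people who do not inject, so the error runs in one direction, against the DAA. The stake is whether a shortfall from 90% can be read as reduced efficacy or partly reflects new infection.

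**Working it through.** **Inputs from the protocol.** n = 100, reference SVR 90%, tolerated difference 10 points, alternative 80%, two-sided alpha 0.05, stated power 85% (Section 13.2); RNA measured 12 weeks after therapy (Section 1.1).

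**Input assumed.** The protocol gives no reinfection rate. I take 5, 10, 20 and 30 per 100 person-years, constant over the 12 weeks from end of therapy to the test. Later infections do not affect SVR12.

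**The plan's own figure.** One-sample normal approximation with null 90%, truth 80%:

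- standard error under the null: √(0.9 × 0.1/100) = 0.03
- standard error under the alternative: √(0.8 × 0.2/100) = 0.04
- power = Φ((0.10 − 1.96 × 0.03)/0.04) = Φ(1.03) = 84.9%

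This reproduces the stated 85%. The exact binomial test at the same values gives 80.8% and rejects on the low side at 83 or fewer responders.

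**Size of the shift.** The fraction reinfected in the window is q = 1 − exp(−rate × 12/52). Only people otherwise counted as responders can lose SVR12 this way, so the loss in points is 100 × (true cure) × q. For example, at 10 per 100 person-years q = 1 − exp(−0.10 × 12/52) = 2.28%, and 90 × 0.0228 = 2.05.

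| Assumed rate per 100 person-years | q | Points lost, cure 90% | Expected SVR12 | Chance of 83 or fewer responders |
|---|---|---|---|---|
| 0 | 0 | 0 | 90.0% | 2.1% |
| 5 | 1.15% | 1.03 | 89.0% | 4.7% |
| 10 | 2.28% | 2.05 | 88.0% | 9.0% |
| 20 | 4.51% | 4.06 | 85.9% | 23.6% |
| 30 | 6.69% | 6.02 | 84.0% | 43.6% |

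**Effect of missing data.** Suppose 10 of the 90 cured participants have no SVR12 test. They are failures already, so only 80 can lose SVR12 through reinfection. The loss becomes 80 × q: 0.92, 1.83, 3.61 and 5.35 points.

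**Against sampling error.** With 90 responders of 100, the exact 95% interval is 82.4% to 95.1%. A shift of 1 to 2 points is small beside that. A shift of 6 points is more than half of the 10-point tolerance.

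**The case against.** The strongest reply is that counting any viraemia as non-SVR is a conservative and defensible primary analysis. It also suits the design as the protocol describes it: the evaluation of a model of care, whose primary hypothesis (Section 3.4) covers both cure and reinfection. At 5 to 10 per 100 person-years the effect is well inside the confidence interval. The last column of the table presupposes a formal test against 90%, whereas Section 13.1 specifies only a proportion with an exact interval. All of this stands. It supports leaving the primary analysis alone. It does not remove the case for a supplementary analysis, because the stated primary objective is efficacy of the drugs.

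A reader might infer more than the documents support:

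- *That the plan expressly scores reinfection as failure.* It does not. The scoring follows from the RNA-only definition and the absence of any other rule.
- *That early reinfections drop out of the exploratory reinfection rate.* That objective concerns reinfection after treatment, not after SVR, and the sequencing trigger also starts at completion of treatment. Nothing excludes cases before SVR12; what is missing is a stated start of time at risk.
- *That relatedness of strains was never considered.* Section 8, item A, foresees comparing it. The gap is that Section 13 does not use the result.
- *That the sequencing is already funded.* The protocol plans it and says nothing about its funding.

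**Conclusion.** The point holds as a gap in the analysis plan, not as an error in the primary analysis. Followed as written, a cured participant who is reinfected before the SVR12 test lowers the DAA efficacy estimate, and the planned sequencing that could identify such cases is not used in Section 13.

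At a true cure rate of 90% the downward shift is about 1.0 to 6.0 points for assumed rates of 5 to 30 per 100 person-years, and 1 to 2 points for 5 to 10. It is smaller where missing data have already made participants failures. The size rests wholly on the assumed rates, a constant hazard and a 12-week window. A test done later than 12 weeks would lengthen that window. The direction does not depend on the rates.

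**What to change.** Keep SVR12 with missing counted as failure as the primary analysis. Add to Section 13.1 wording along these lines:

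*Participants viraemic at the SVR12 test will be classified by comparing baseline and post-treatment sequences as virologic failure (same strain), reinfection (different genotype or unrelated strain) or indeterminate. As a prespecified supplementary analysis, SVR12 will also be reported with confirmed reinfections counted as cured of the baseline infection; indeterminate cases remain failures.*

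Name this use of the sequences in Section 6.3.7. For exploratory objective 1, state that time at risk starts at end of therapy, so that reinfections before SVR12 are counted. The classification should be fixed before results are seen, since sorting failures afterwards invites bias.

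The cost is a few sentences and one extra reported row. There are limits. Some cases will stay indeterminate, and reinfection with a closely related strain can be misread as relapse. A scheduled stored sample (Section 6.3.4) coincides with the SVR12 visit, at week 24, only for 12-week courses, and Section 3.2.1 fixes no course length; Section 6.3.7 nevertheless sends a current sample in any case.

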4.4 Vulnerable/Incarcerated Participants

Because of the high rates of incarceration amongst people who use drugs, it is possible that participants will become incarcerated during the course of the study. While we will not enroll participants during a time of incarceration, participants will not be removed from the study if the

study team becomes aware of their incarceration during the study period. This will enable the study team to continue to provide direct acting antiviral medication to the participants, which would not be possible if the participant is removed from the study. In this way, ongoing inclusion in the study will benefit the participant, even during this vulnerable time. Participants will have the right to refuse treatment during incarceration.

Participants who become incarcerated during the course of the study will not have study data collected during their incarceration. In the cases where the study team is made aware of a participant's incarceration while they are on active HCV treatment (taking direct acting antiviral therapy at the time of incarceration), the study team will make a reasonable effort to deliver the remaining course of HCV treatment to the jail/prison so the participant can have the best chance of being cured for hepatitis C and does not develop resistance to hepatitis C medication.

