13.2 Sample Size Justification

Based on the available DAA drugs, we expect to be able to treat up to 200 patients for HCV, with primary efficacy analysis after the first 100 enrolled participants (phase 1). The SVR of the general US population for HCV-infected and non-injection drug users is estimated at >90%. We target in our population of injection-drug users no greater than a $\pm 10\%$ SVR difference from the standard 90% SVR. For the primary objective, we will have 85% power to reject the null hypothesis if the actual proportion of patients with SVR is 80% or higher at a 2-sided, $\alpha=0.05$ significance level.

14 Ethics/Protection of Human Subjects

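### Missing=failure is a defensible primary outcome for a model of care, but as the only SVR12 estimate it cannot separate DAA efficacy from retention

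*Combined protocol and SAP*

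**What the plan says.** Section 2.1 makes the efficacy of DAAs the primary objective, and section 3.1 describes the study as an evaluation of a model of care. Section 13.1 defines the primary efficacy analysis as the SVR12 proportion in the first 100 participants, with an exact two-sided 95% confidence interval, among all who took at least one DAA dose. On missing outcomes it says only that "patients without follow-up data are considered to have treatment failure". It plans no observed-data or sensitivity analysis, gives no rule for a later HCV RNA result, and does not split non-SVR by cause.

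Section 13.2 sets the reference: "The SVR of the general US population for HCV-infected and non-injection drug users is estimated at >90" percent. It aims for at most a 10-point "SVR difference from the standard 90% SVR" and states that "we will have 85% power to reject the null hypothesis if the actual proportion of patients with SVR is 80% or higher", two-sided at 0.05. It gives no expected loss to follow-up and no allowance for it in the sample size.

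Section 4.4 says: "Participants who become incarcerated during the course of the study will not have study data collected during their incarceration". The same section commits the team to a reasonable effort to deliver the rest of the DAA course to the jail or prison. Section 10 says: "If a patient becomes pregnant during the course of the study, the patient will be discontinued from the study". Section 10.1 does not let withdrawn participants return.

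**The concern.** A participant who is cured but not sampled counts the same as one in whom the drug failed. Section 4.4 makes this concrete: someone could finish the course in custody, be cured, and have no SVR12 sample. The resulting proportion combines drug effect and retention. If it is then read as DAA efficacy against 90%, a shortfall caused by lost contact could be taken as evidence that DAAs work less well in people who inject drugs. Section 1.4 says this group is largely excluded from care by insurance restrictions and that the study is meant to show treatment is feasible and effective, so that misreading would work against the study's own purpose.

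**Working it through.** **Inputs.** From section 13.2: n = 100, reference 90%, alternative 80%, two-sided alpha 0.05, stated power 85%. From section 13.1: exact (Clopper-Pearson) 95% interval, missing = failure. Assumed, because the documents give neither: true SVR of 90% or 95% (sections 1.3 and 13.2 say above 90%), and loss of 0 to 15%, independent of cure.

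**Step 1: the plan's own power figure.** Score test, normal approximation, null 90%, true rate 80%:

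Power = Φ[(|p1 − p0| − 1.96·√(p0(1−p0)/n)) / √(p1(1−p1)/n)] = Φ[(0.10 − 1.96 × 0.03) / 0.04] = Φ(1.03) = 0.8485.

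This matches 85%. The other two-sided versions checked do not:
- 90% against 80%: continuity-corrected 0.817, arcsine 0.810, exact 0.808, Wald 0.705.
- Null 80% with true 90%: score Φ[(0.10 − 1.96 × 0.04) / 0.03] = Φ(0.72) = 0.764; exact 0.703.
- Null 70% with true 80%: score 0.60.

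The figure therefore points to a null of 90%, with rejection meaning a shortfall. That is an inference; the plan does not write the null.

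**Step 2: cut-offs for the exact interval at n = 100.**
- 83/100 gives 74.2% to 89.8%, and 84/100 gives 75.3% to 90.6%. The interval lies wholly below 90% at 83 or fewer.
- 88/100 gives 79.98% to 93.6%, and 89/100 gives 81.2% to 94.4%. The lower limit exceeds 80% at 89 or more.

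**Step 3: effect of loss.** With loss m independent of cure and true SVR v, the expected missing=failure SVR is p = v(1 − m). With X ~ Binomial(100, p):

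| True SVR | Loss | p | P(X ≤ 83): interval below 90% | P(X ≥ 89): lower limit above 80% |
|---|---|---|---|---|
| 90% | 0% | 0.900 | 2.1% | 70.3% |
| 90% | 5% | 0.855 | 27.7% | 20.0% |
| 90% | 10% | 0.810 | 73.3% | 2.3% |
| 90% | 15% | 0.765 | 95.5% | 0.1% |
| 95% | 0% | 0.950 | 0.0% | 99.6% |
| 95% | 5% | 0.9025 | 1.6% | 73.2% |
| 95% | 10% | 0.855 | 27.7% | 20.0% |
| 95% | 15% | 0.8075 | 75.3% | 2.0% |

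**Step 4: the independence assumption.** If everyone lost was uncured, missing=failure scores them correctly, p = v, and the chance of a shortfall finding stays at its no-loss value (2.1% at true SVR 90%). With 10% loss and true SVR 90%, the figure therefore runs from 2.1% (all lost uncured) to 73.3% (loss independent of cure). This protection is limited by the uncured share: at true SVR 95% only 5 in 100 are uncured on average, so at 10% loss about half or more of those lost must have been cured.

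**Step 5: the plan's 10-point tolerance.** Expected SVR drops to 80% when m = 1 − 0.80/v, which is 11.1% loss at true SVR 90% and 15.8% at true SVR 95%.

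**The case against.** A reader might infer that missing=failure is simply the wrong rule, or that modest loss would by itself make effective DAAs look inferior. The documents do not support either.

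- **No null or decision rule is written.** Section 13.1 plans a proportion and an interval, not a test against 90%. Taken literally, the words about 80% or higher in section 13.2 make rejection the favourable result, and the rule is then conservative. The plan never calls the rule conservative either. This stands, so the shortfall figures hold only under the inferred null.
- **The plan tolerates a 10-point difference.** An SVR of 80 to 90% is within target, and expected SVR leaves that range only at losses above 11.1% or 15.8%. This stands too.
- **The outcome depends on unknowns.** At true SVR 95% and 5% loss the false-shortfall chance is 1.6%, and it is smaller still where those lost were mostly uncured. The claim is that retention could decide the result, not that it would.
- **The protocol limits missingness.** Section 4.4 stops data collection only during incarceration and does not remove the participant. Section 6.7 offers continued follow-up after early discontinuation and documents the reason. HCV RNA is measured again at later visits, and someone with a later result might not count as lacking follow-up data. The last point is a possible reading of 13.1, not something it says.
- **Non-retention is a legitimate failure for a model of care.** Agreed, and a reason to keep the rule as primary.

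These limits narrow the point without removing it. If success means a lower limit above 80%, the rule cannot overstate SVR, but it can hide an effective drug: the last column of the table falls from 70% to 20% with 5% loss at true SVR 90%.

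**Conclusion.** The point holds in this form: missing=failure is acceptable as the primary outcome, but used alone it cannot answer the efficacy question in section 2.1, and it is biased downward for efficacy whenever some of those lost were cured. Under either reading of section 13.2, retention alone could settle the result:

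- **Inferred null of 90%:** the chance of a false shortfall at 10% loss is 73% if true SVR is 90% and 28% if it is 95%.
- **Success as a lower limit above 80%:** the chance of success at true SVR 95% falls from 99.6% with no loss to 20% with 10% loss.

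These sizes rest on n = 100, the assumed true SVR and loss rates, and loss independent of cure; if all those lost were uncured, the inflation disappears. The rule should be called anti-conservative only for concluding a shortfall from 90%, never for a claim that DAAs work. The absence of any supplementary estimate or loss assumption does not depend on these figures.

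**What to change.** Amend section 13.1 as follows.

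1. Keep missing=failure as the primary estimate.
2. State that, when the SVR12 sample is missed, an undetectable HCV RNA at any later scheduled visit counts as SVR. Weeks 48, 72 and 96 are available now. Week 36 is listed in section 6.3.6 but has no HCV RNA entry in Appendix B, so the two must be reconciled before it is used.
3. Add a pre-specified SVR12 proportion with exact 95% interval among participants with any HCV RNA at least 12 weeks after the last dose. Label it a sensitivity estimate, not an upper bound: if those lost were cured more often than those seen, the true rate lies above it. If bounds are wanted, use missing=failure and missing=success.
4. Tabulate non-SVR as virologic failure, reinfection (using the sequencing in section 6.3.7) or missing, with the reason.
5. Base any statement on DAA efficacy against 90% on both the primary and the observed-data estimate.

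The cost is one further estimate, one table and a sentence on late results, all from samples and sequencing already planned. The downside is that the observed-data estimate may be optimistic if those lost were less often cured, which is why it sits beside the primary estimate and does not replace it.

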5 INTERVENTIONS

5.1 Assessment of Subject Adherence

Adherence will be assessed by subject interview and pill count as per study schedule.

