6.3.1 Adherence monitoring

On weeks 4, 8, 12 participants will meet with study staff to complete counts of remaining pills, as well as answering questions regarding HCV treatment adherence.

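### Section 13.1 offers only chi-squared or Fisher's exact test for adherence against SVR12; if the pill count is cut into groups, a graded relation is tested with less power, by an amount that depends on assumptions, and the cut is left open

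*Combined protocol and SAP*

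**What the plan says.** Section 13.1 (Description of the Analyses) sets the test: "Chi-squared or Fisher's exact test will be used to assess the association of SVR12" with baseline characteristics such as HIV status, "as well as on treatment factors such as medication adherence and OST status". No other method is given for relating HCV-treatment adherence to cure.

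On measurement, section 5.1 states "Adherence will be assessed by subject interview and pill count as per study schedule". Section 6.3.1 adds the timing: "On weeks 4, 8, 12 participants will meet with study staff to complete counts of remaining pills", together with questions about adherence.

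The documents do not say how interview and pill count combine into one variable. They give no category, cut point, trend test, rank test or regression model for it. Section 2.3 lists "Evaluate adherence to HCV medications" as exploratory objective 4. The analysis set is taken here as phase 1, because 13.1 says "The primary outcome is achievement of SVR12 in phase 1 (first 100 enrolled participants").

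**The concern.** Both named tests need categories, whereas a count of remaining pills converts naturally to a percentage of doses taken. Applying the tests to that percentage means cutting it, which discards the ordering within groups. Outcome information is already thin: with 100 participants and an SVR12 of 80 to 90%, only 10 to 20 people fail.

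Two things are at stake. A real gradual relation is more likely to be missed, and a non-significant result could then be read as evidence that adherence made no difference. And because no cut is fixed, it could be chosen after the outcomes are known, which inflates the false-positive rate.

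**Working it through.** **The plan's own power figure.** The only one is the 85% in section 13.2, for the one-sample test of SVR12. With null 0.90, truth 0.80, n = 100 and two-sided 0.05:

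Φ[(0.10 × √100 − 1.96 × √(0.9 × 0.1)) / √(0.8 × 0.2)] = Φ[(1 − 0.588) / 0.4] = Φ(1.03) = 84.9%.

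It reproduces, but says nothing about adherence; no power is stated for that test.

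**Inputs.** From the documents: n = 100 (13.1), SVR12 of 80% and 90% (13.2), and two-sided 0.05 (stated in 13.2 for the primary objective, assumed here). Assumed, because the documents give nothing: the adherence distribution, the strength of the relation and the cut. SVR12 follows a logistic model on standardised adherence. Chi-squared is used when every expected count is at least 5, otherwise Fisher.

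**Graded relation, 0.7 to 0.8 log-odds per SD, adherence Beta(6, 1.2)** (median 86%, a third below 80%). Power:

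| Test | SVR 80% | SVR 90% |
|---|---|---|
| Wilcoxon, full scale | 76–86% | 56–69% |
| Cut at 80% | 68–78% | 43–54% |
| Cut at median | 59–70% | 33–41% |
| Cut at 90% | 46–58% | 22–28% |
| Cut at 95% | 14–21% | about 2% |

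Against the 80% cut the loss is 8 points at SVR 80% (76 − 68; 86 − 78) and 13 to 15 at SVR 90% (56 − 43; 69 − 54). Over this shape, Beta(4, 1), and 30% fully adherent with the rest Beta(5, 1.2), the loss is about 6 to 15 points; one run of Beta(4, 1) at SVR 90% came nearer 20. Cuts at the median or above lose 16 points or more in the table.

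**Two checks by hand.**
- Median split: a normal variable correlates √(2/π) = 0.798 with its own median split. For normal adherence, SVR 80% and 0.7 per SD, simulated logistic power is 76%, a shift of 1.96 + 0.706 = 2.666. Then 2.666 × 0.798 = 2.127, and Φ(2.127 − 1.96) = 57%. The simulated median-split chi-squared gave 55%.
- 95% cut: about 81% of Beta(6, 1.2) lies below 0.95, leaving about 19 participants above. With 10 failures, even none among those 19 has one-tail probability C(81,10)/C(100,10) = 0.11, so with these margins Fisher cannot reach 0.05 in the expected direction.

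**Where the loss is small.**
- Weak effect (0.3 per SD), Beta(6, 1.2): Wilcoxon 22% against 19% for the 80% cut (SVR 80%), and 14% against 12% (SVR 90%). Both tests are underpowered.
- 60% fully adherent, 0.75 per SD: 81% against 80%, and 68% against 65%.
- Over such settings the gap to an 80% cut is about 1 to 5 points.
- A four-level measure with all levels kept: a loss of −2 to 6 points.

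**Where the categorical test wins.** With a true step exactly at 80%, the 80% cut has 92% against 82% for Wilcoxon (SVR 80%) and 78% against 67% (SVR 90%). A 90% cut on the same data has only 50% and 31%.

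**Open choice of cut.** With no true relation, taking the smallest p-value over cuts at 80%, 90%, 95% and the median rejects in about 7 to 13% of trials, against about 5% for Wilcoxon.

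**Missing pill counts.** If half of the failures had no pill count (assumed), full-scale Wilcoxon power at 0.75 per SD falls by about 25 points, to roughly 55–58% (SVR 80%) and 36–38% (SVR 90%).

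**The case against.** The strongest reply is that the analysis variable is being inferred. The documents never define HCV adherence as a percentage of doses. Interview answers form part of it, and it could be recorded in a few ordered levels. This stands: a reader might infer that the plan forces adherence to be dichotomised, but the documents do not say so, and with all levels of an ordered measure kept the loss is close to nil.

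Second, no power-loss figure comes from the documents. This also stands. A flat claim of 5 to 20 points or more would be too strong, since plausible inputs bring the gap over an 80% cut down to 1 to 5 points. The largest losses come from cuts nobody has proposed.

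Third, a reader might take adherence and cure to be a central question, because the précis mentions concern about adherence as a reason for insurance restrictions. That is background. The matching objective is exploratory, no listed objective names an adherence–SVR12 association, and with 10 to 20 failures no test could establish that adherence has no effect.

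Fourth, 13.1 counts participants without follow-up data as failures, and the same people may not have returned pills. A full-scale analysis does not cure that, so the fix must address it.

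What remains is that the only tests named do not suit a pill count, and no coding is fixed.

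**Conclusion.** The point holds as a minor one. If the pill-count percentage is grouped and the relation is graded, the planned tests lose power against a rank or logistic analysis: about 1 to 5 points with weak effects or mostly full adherence and an 80% cut, about 6 to 15 points at 0.7 to 0.8 log-odds per SD against an 80% cut, and 20 or more with poor cuts. Choosing among several cuts after the data are seen raises type I error to about 7 to 13%.

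These sizes rest on assumed adherence distributions, effect sizes and cuts, and on complete pill counts for 100 participants. The direction is stable for graded relations; it reverses when a cut falls exactly on a true step.

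The primary SVR12 proportion and its exact confidence interval are untouched. Nor do the documents show that any cut has been, or will be, picked after the fact; they only leave that possible.

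**What to change.** In section 13.1:

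- Relate pill-count adherence (percent of prescribed doses taken) to SVR12 on its full scale by Wilcoxon rank-sum test and logistic regression, using Firth's method if failures are few, with an odds ratio per 10 percentage points and its 95% confidence interval.
- Show SVR12 by adherence category descriptively, with the categories fixed in advance.
- Report how many participants have no pill count, separately for those counted as failures because follow-up is missing, and repeat the analysis among those with an observed SVR12.
- Keep chi-squared or Fisher's exact test for categorical factors such as HIV status and OST status.

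The cost is a few sentences. Pill counts and SVR12 are already collected and no visit changes. The one downside is less power if the true relation is a step exactly at the chosen cut; the descriptive table would still show such a step.
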